The trial is being conducted in nine homeless shelters in the Seattle, WA metropolitan area. The aim is to enroll nine shelters, each with a nightly population of between approximately 45 to 212 individuals for a total number of a maximum 1,696 individuals under surveillance each influenza season. We will conduct this trial over two influenza seasons with re-randomization of the shelters each season for timing of the intervention. The University of Washington is the sponsor of the trial which is supported by an anonymous funder who does not have any ownership over the management and conduct of the study, the data, or the rights to publish.

III. Objectives

The objective of the trial is to evaluate the efficacy of on-site testing and rapid antiviral treatment with baloxavir or oseltamivir in influenza-positive individuals for prevention of secondary cases of influenza virus infection within homeless shelters.

Primary Outcome Measure

The primary outcome measure will be the incidence of cases of influenza in shelters during the intervention period compared to the incidence of cases during the control period. It will be calculated as the number of cases of laboratory-confirmed influenza among shelter residents divided by the number of unique shelter residents tested. The incidence during intervention periods will be compared to the incidence during non-intervention periods using a generalized linear mixed model to control for clustering, differences in shelters, and time period.

Secondary Outcome Measures

Feasibility and adherence outcomes

- Feasibility of implementation of point-of-care molecular testing and treatment of influenza in shelters (time between symptom onset until diagnosis)
- Feasibility of implementation of influenza treatment in shelters (time between symptom onset until treatment)
- Proportion of participants that become lost to follow-up (after testing positive for influenza at baseline enrollment and receiving an antiviral)
- Proportion of participants that show non-compliance with study drug (only applicable to oseltamivir)

Clinical outcomes

- Symptom type, duration and severity among viral positive cases (including broken down by influenza sub-type)
- Prevalence of asymptomatic and pauci-symptomatic influenza-positive cases
- Proportion of laboratory-confirmed influenza cases that report fever
- Relationship between symptom type, duration and severity, and current seasonal influenza vaccination status

Laboratory outcomes

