Person-to-person transmission: We will use the CDC definition for influenza transmission that refers to the ability of an influenza virus to spread from one person to another, most commonly through large or small droplets containing influenza virus that are expelled when a sick person is coughing or sneezing.

Homelessness: We will use a truncated version of the definition provided by the U.S. Department of Housing and Urban Development that identifies people who are living in a place not meant for human habitation, in emergency shelter, in transitional housing, or are exiting an institution where they temporarily resided if they were in shelter or a place not meant for human habitation before entering the institution.

X. Statistical analyses

Due to the SARS-CoV-2 pandemic onset and corresponding methodological changes, the primary outcome measure for this study will only be calculated based on data collected from Year 1. Standard surveillance beginning on March 30, 2020 expanded to include the testing of study staff and

asymptomatic individuals 3 days per week. The primary outcome measure will be calculated excluding asymptomatic individuals and shelter staff tested as part of the modified standard surveillance methodology initiated on March 30, 2020. As shelter managers were unable to provide us with reliable daily census, we were unable to establish person-days at risk for this study population. Instead, we will use unique participants as the primary unit of analysis. Overall, data collected between November 15, 2019 and March 31, 2021 will be used for data analysis.

Primary Outcome Measure

1. **Cumulative incidence** of cases of influenza (A and B) in shelters during the intervention period compared to the control period.
 - a. As daily census counts for participating shelters were not made available to the research team, person-days and therefore incidence rates will not be calculable. Cumulative incidence instead will be calculated as the number of cases of laboratory-confirmed influenza among shelter residents divided by the number of unique shelter residents tested.

Endpoint: Number of influenza-positive events in the control v. intervention periods

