Statistical analysis: Shelters will be analyzed with an intent to treat analysis to preserve the advantages of randomization. The number of influenza-positive tests will be analyzed using a generalized linear mixed model following a Poisson distribution with a log link and robust variance. The model is adjusted for calendar time and an exposure time variable based on shelter capacity. It will be used to calculate the relative risk of infection during the intervention period compared to prior to intervention, 95% confidence intervals, and p-value.

This model includes symptomatic individuals who tested throughout Year 1 of the study (November 15, 2019 – March 31, 2020).

Despite operational futility, descriptive statistics (counts, proportions, and appropriate measures of dispersion) for **both years 1 and 2** will be provided for the following Secondary Outcome Measures; additional statistical models will not be run due to low influenza case counts and the impact of the SARS-CoV-2 pandemic:

1. Feasibility of implementation of point-of-care molecular testing and treatment of influenza in shelters
 - a. Proportion of participant encounters with time between symptom onset until diagnosis with RT-PCR <48 hours in each study period
2. Feasibility of implementation of influenza treatment in shelters
 - a. Proportion of influenza-positive participants identified through on-site molecular testing in the intervention period that were treated with an antiviral
3. Proportion of participants that drop out of study
 - a. Measured as dropping out after providing consent
4. Proportion of participants that show non-compliance with study drug

- a. Only applicable to those that receive oseltamivir rather than baloxavir which is a single-dose antiviral. Measured based on self-report during follow-up visits with study research assistants.
5. Proportion of laboratory-confirmed influenza cases that report fever, or feverishness
 - a. Based on self-report, not gold standard measurement
6. Influenza viral RNA levels
 - a. Measured mean cycle threshold value for each laboratory-confirmed influenza-positive specimen collected at baseline enrollment
7. Proportion of samples with detectable influenza RNA virus at days 2/3 and days 5/6/7
 - a. Provided subject has not become lost to follow up

XI. Data Safety and Monitoring

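### The primary model counts positive tests while the outcome counts cases among unique residents, and only treated intervention-period cases have scheduled repeat swabs

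*Combined protocol and SAP*

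**What the plan says.** All references are to the combined protocol and SAP.

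**The count**
- Section X, opening paragraph, after noting that no reliable daily census was available: "Instead, we will use unique participants as the primary unit of analysis".
- Section X, Primary Outcome Measure: "the number of cases of laboratory-confirmed influenza among shelter residents divided by the number of unique shelter residents tested". Section III gives the same definition.
- Section X, Endpoint: "Number of influenza-positive events in the control v. intervention periods".
- Section X, Statistical analysis: "The number of influenza-positive tests will be analyzed using a generalized linear mixed model". The same paragraph adds "The model is adjusted for calendar time and an exposure time variable based on shelter capacity" and "It will be used to calculate the relative risk of infection during the intervention period compared to prior to intervention". The only stated limit on the model's data is to symptomatic individuals tested in Year 1, 15 November 2019 to 31 March 2020.

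**The swabs**
- Table 2 (Section VIII) gives the control period an enrollment swab only. The intervention period has day 0, day 2/3 and day 5/6/7.
- Section V, Intervention period, item 13 makes the later swabs follow drug receipt. The pre-intervention text says that no treatment is offered in that period.
- Section VI sends the day 2/3 and day 5/6/7 swabs to the laboratory.
- Secondary measure 7 in Section X uses them: "Proportion of samples with detectable influenza RNA virus at days 2/3 and days 5/6/7".

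**The concern.** The response named in the model sentence is what an analyst will program. Counting positive tests is not the same as counting cases or participants, and here the difference is not balanced between periods. The extra laboratory swabs from one illness arise only after treatment, so only in the intervention period.

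Nothing else in the model would offset the extra positives. Shelter capacity does not grow when a known case is swabbed again, nor does the number of unique residents tested. Robust variance changes the standard error and leaves the point estimate where it is. What is at stake is a primary RR that partly reflects the swabbing schedule and understates any benefit.

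**Working it through.** The plan gives no figure for this point, so there is none to reproduce. The check is a comparison of the passages, followed by the algebra.

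**Step 1. Are the repeat swabs confined to the intervention period?** Section VI schedules them for flu-positive individuals without naming a period. Table 2 and item 13 confine them to treated cases. Section VIII, Return of Results, supports this: laboratory influenza results take about 7 days or more, so a control-period positive would not be known in time to prompt a day 2/3 swab.

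**Step 2. Does any rule remove them from the primary count?**
- The Year 1 and symptomatic restriction selects people and dates, not visits or swabs.
- Section IX separates influenza-like illness episodes by 14 days from the last enrollment. That would absorb day 2 to day 7 swabs, but it is written for influenza-like illness, while enrollment uses cough or ARI symptoms, and Section X does not cite it.
- The two-week limit in Section V, Pre-intervention period, concerns participation, not scheduled follow-up.
- Secondary measure 6 is restricted to specimens from baseline enrollment. The primary measure carries no such restriction.

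No sentence excludes them.

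**Step 3. Effect on the RR if tests are counted literally.** Let s_I and s_C be the mean number of extra laboratory positives per case in the intervention and control periods. Expected counts are multiplied by (1 + s_I) and (1 + s_C). If these multipliers are constant, the log link gives

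apparent RR = true RR × (1 + s_I)/(1 + s_C).

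The intervention term has two parts, s_I = u + e_I:
- u = f × r × (p1 + p2), from follow-up swabs. Here f is the share of intervention-period cases treated, r is follow-up attendance, and p1 and p2 are laboratory positivity at day 2/3 and day 5/6/7.
- e_I comes from repeat enrollments. The control term s_C comes from repeat enrollments only.

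By schedule, u lies between 0 and 1 × 1 × (1 + 1) = 2. None of f, r, p1, p2, e_I or s_C is in the documents. The values below are assumptions that show how the factor behaves:

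| s_I | s_C = 0 | s_C = 0.1 | s_C = 0.2 |
|---|---|---|---|
| 0.1 | 1.10 | 1.00 | 0.92 |
| 0.2 | 1.20 | 1.09 | 1.00 |
| 0.5 | 1.50 | 1.36 | 1.25 |

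For example, 1.5/1.1 = 1.36. Any u above 0 raises the factor above what it would be without follow-up swabs. The net factor also depends on s_C.

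**Step 4. One count per person, enrollment swab only.** Follow-up swabs add nothing, so u = 0 and the repeat-swab bias is zero.

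**The case against.** The strongest reply is that Section X already settles the matter. The unit is unique participants, the outcome is cases, and the model is said to estimate a relative risk of infection. A second swab from a known case is not a new participant, case or infection. An outcome, an endpoint label and a unit of analysis may also properly carry different names, so only the word *tests* is out of line. Follow-up data sit in a separate REDCap survey (Section VIII) and have their own secondary measure.

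Most of this stands. It makes one count per person the likely intent. It does not change what the model sentence says, and the unique-resident denominator that would point to one count per person is replaced in the model by a capacity-based exposure term.

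Two stronger readings are tempting, and the documents support neither.
- A reader might take 1 to 3 as the range of distortion, from u between 0 and 2. That range ignores repeat positives among control residents who re-enroll. Its upper end also needs every intervention-period case to be treated, to attend both visits and to test positive each time. Cases with 3 to 7 days of symptoms receive no on-site test or drug.
- A reader might infer that the design effect, an RR of 0.50, would be hidden entirely. With s_C = 0, that needs an average of one extra positive per intervention-period case, untreated cases included, and the documents give no such value. The RR of 0.50 with 86% power also belongs to 18 shelter-seasons, whereas the primary analysis now uses Year 1 only.

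**Conclusion.** The point holds as a conflict between the stated model response and the plan's own outcome definition. It should be fixed, but it is not evidence that the result is biased. If tests were counted literally, follow-up swabs would move the RR upward and could mask a benefit; on their own they could not create one. The size cannot be fixed from the documents. If follow-up swabs are left out, as is probably intended, this bias is zero.

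The wording conflict and the one-sided swab schedule are certain from the text. The bias is conditional on how the model sentence is carried out. The factor assumes that extra positives per case are roughly constant within each period.

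**What to change.** 1. In Section X, Statistical analysis, define the response as the number of residents with a laboratory-confirmed influenza-positive enrollment (day 0) swab, each counted at most once per period (control or intervention), with the same rule in both periods.
2. State that day 2/3 and day 5/6/7 swabs are excluded from the primary count and used only for secondary measure 7.
3. Use the same term in the Endpoint line.
4. Record the change as made after data collection. This version is dated March 2022, the model's data end on 31 March 2020, and Section X already describes the missing census in the past tense.

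The cost is a few sentences and one de-duplication step. Section VIII already links follow-up swabs by study ID and checks IDs that have several enrollments. No new data are needed and no study procedure changes.

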RR	.7	21	31	36	41	51	63
	.65	27	40	48	54	65	77
	.6	34	51	60	67	77	88
	.5	52	72	81	86	93	98

Assuming nine shelters participating for two seasons each (18 shelter-seasons), we would have an estimated 86 percent power to detect a risk ratio of 0.50 at a 0.05 two-sided significance

level, and assuming 200 participants per shelter. The incidence during intervention periods will be compared to the incidence during non-intervention periods using general estimating equation models to control for clustering, differences in shelters, and time period. Power calculation details can be found in **Additional File 2**.

Individual enrollment criteria

Participants must fulfill all of the following inclusion criteria:

- Resident for 1 or more days at a participating shelter
- 3 months or older
- Acute cough or ≥ 2 ARI symptoms (see **Table 1** for list)
- Willing to take study medication
- Willing to comply with all study procedures, including weekly surveillance and repeat nasal swab at day 2/3 and day 5/6/7 post-treatment.
- Able to provide written, informed consent and/or assent

Table 1 – ARI trigger symptoms (participants should have ≥ 2 or more of the following new symptoms for eligibility within the past 7 days during the control period and within the past 48 hours during the intervention period)

Feeling feverish	Runny or stuffy nose
Headaches	Increased trouble with breathing
Cough	Fatigue (tiredness)
Sore throat or itchy/scratchy throat	Muscle or body aches
Nausea or vomiting	Diarrhea**
Rash**	Ear pain or ear discharge**

** *Only if under 18*

Exclusion criteria

Individuals meeting any of the following criteria will be excluded:

- Any serious or uncontrolled medical disorder or active infection that, in the opinion of the investigator, may increase the risk associated with study participation or study drug administration

- Inability to consent and/or comply with study protocol
- Individuals who have received oseltamivir or baloxavir within past 7 days for treatment of influenza
- Individuals with known hypersensitivity to baloxavir marboxil or oseltamivir
- Individuals with chronic kidney disease (CKD)

Withdrawal criteria

All participants are free to withdraw from the study at any time. Additionally, it is within the rights of the PI to withdraw any participant at any time during the study at her discretion.

Additional consent concerns

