Shelters will be randomized to different starting months for the intervention. Kiosks will continue to be staffed at regular times 6 days a week during the intervention period at each shelter. The intervention will include on-site molecular testing for influenza with the Abbott device and baloxavir (XOFLUZA) treatment for all influenza-positive individuals 12 years of age and older who weigh >40 kg, are not pregnant or breastfeeding, and do not have active malignancy, liver disease, or are immunocompromised. Individuals who meet inclusion criteria will have a nasal swab collected. Individuals with positive results who are Baloxair-eligible will be provided with a one-time dose of baloxavir. As baloxavir is an FDA-approved drug for

influenza treatment and considered standard-of-care, there will be no placebo introduced to the control groups. The description of the antiviral from the product monograph is as follows:

XOFLUZA™ is a polymerase acidic (PA) endonuclease inhibitor indicated for the treatment of acute uncomplicated influenza in patients 12 years of age and older who have been symptomatic for no more than 48 hours.

Limitations of Use: Influenza viruses change over time, and factors such as the virus type or subtype, emergence of resistance, or changes in viral virulence could diminish the clinical benefit of antiviral drugs. Consider available information on drug susceptibility patterns for circulating influenza virus strains when deciding whether to use XOFLUZA.

All influenza-positive individuals aged 3 months to 11 years, who are pregnant or breastfeeding, and adults with active malignancy, liver disease, or who are immunocompromised (Table 3) will be provided with a 5-day supply of oseltamivir. The antiviral description from the product monograph is as follows:

Oseltamivir (also known as the marketed product TAMIFLU®), is an antiviral neuraminidase inhibitor used for the treatment and prophylaxis of infection with influenza viruses A (including pandemic H1N1) and B. Oseltamivir exerts its antiviral activity by inhibiting the activity of the viral neuraminidase enzyme found on the surface of the virus, which prevents budding from the host cell, viral replication, and infectivity.

Table 3. Pre-existing conditions that necessitate oseltamivir dosage

Immunosuppression (by medication or disease)
Cancer
Liver disease

The enrollment process for participants during the intervention period is as follows:

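### The primary p-value and 95% CI rest on a robust variance from nine shelters, with no clustering level, small-sample method, reference distribution or form of calendar time stated

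*Combined protocol and SAP*

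**What the plan says.** The primary analysis in Section X (Statistical analyses) is a "generalized linear mixed model following a Poisson distribution with a log link and robust variance". It yields the relative risk, its 95% CI and the p-value. On covariates Section X adds only this: "The model is adjusted for calendar time and an exposure time variable based on shelter capacity". It also says that "the primary outcome measure for this study will only be calculated based on data collected from Year 1", and the model uses symptomatic people tested from November 15, 2019 to March 31, 2020. The Summary and Section II give nine shelters. Section V (Intervention period) says: "Shelters will be randomized to different starting months for the intervention".

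Section III (Primary Outcome Measure) agrees on the type of model: a "generalized linear mixed model to control for clustering, differences in shelters, and time period". Section IV (Sample size) describes the same comparison as using "general estimating equation models to control for clustering, differences in shelters, and time period", and sets a two-sided 0.05 level.

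For the secondary outcomes, Section X says that "additional statistical models will not be run due to low influenza case counts". The primary model is therefore the only modelled inference in the trial.

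Nowhere does the document state the clustering level of the robust variance, a small-sample correction, degrees of freedom, a reference distribution or a randomisation test. It does not say whether calendar time enters as month indicators or as a straight line.

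**The concern.** A cluster-robust variance is built from one residual contribution per cluster. With nine shelters there are nine contributions. With five monthly periods as indicators plus the intervention term, six regression coefficients are estimated from the same data. The fit pulls each shelter's residuals towards zero, so the variance is too small on average. It is also noisy, and a normal reference ignores that noise. Both faults push the same way: p-values too small and intervals too narrow.

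At stake is whether the trial's single p-value can be read at the 0.05 level that Section IV sets. The open choices (form of calendar time, clustering, correction, reference distribution) can move that p-value across 0.05. Version 2.8 is dated March 19, 2022, after the primary data window closed, so any choice still unstated could be made with results in view.

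**Working it through.** **1. The plan's own figure.** Section IV states 86% power for RR 0.50 with 18 shelter-seasons. The stepped-wedge formula is power = Φ(|δ|/√V − 1.96). Here δ = 0.016 × (1 − 0.50) = 0.008 per month, and V is the generalised least squares variance with random shelter and shelter-by-month effects and fixed months. With six months, four steps and the stated SDs it gives 85%. At RR 0.60, 0.65 and 0.70 it gives 65, 53 and 40%, against 67, 54 and 41% in the plan. The inputs are therefore read as intended. This formula treats the variance components as known, so it says nothing about the error rate of the robust test.

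**2. Simulation inputs.**
- From the plan: nine shelters; 1.6% per month; shelter CV = 0.0028/0.016 = 0.175; shelter-month CV = 0.0032/0.016 = 0.20; log-capacity offset.
- Assumed: four or five monthly periods (the window is 4.5 months); steps such as 3/2/2/2 or 3/3/3 (the design figure is not shown); a shelter random intercept; season shape.
- Shelter sizes: 200 each (Section IV); 1,032/9 = 114.7 each (Section IV); or Figure 3 capacities A to I, because the nine trial sites are not identified.
- Expected cases at flat incidence over 4.5 months: 1,800 × 0.016 × 4.5 ≈ 130, or 1,032 × 0.016 × 4.5 ≈ 74.

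**3. Test.** Fit log E(Y_ij) = log(capacity_i) + month_j + θX_ij + u_i. Take V = A⁻¹(Σ g_i g_i′)A⁻¹, where g_i is shelter i's score contribution and A is the information matrix. Reject if |θ̂|/√V > 1.96. Data are generated with no effect.

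**4. Type I error, month indicators, uncorrected, normal reference.**

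| Setting | Type I error |
|---|---|
| Mixed model, 200 each (five / four periods) | 13.5 / 13.4% |
| Mixed model, 114.7 each | 13.3 / 13.3% |
| Mixed model, capacities A to I | 15.9 / 16.2% |
| Mixed model, three assumed epidemic peaks | 12.2 to 13.8% |
| Mixed model, separately coded runs, wider assumptions | 12.8 to 17.8% |
| Marginal Poisson fit, plan's rate and SDs | 12 to 18% |

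The first four rows use 10,000 runs per case (Monte Carlo SE about 0.35 points) and the fifth 3,000 (about 0.6 points). The 17.8% in the fifth row comes from heterogeneity larger than the plan's.

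**5. Hand check.** The robust SE averaged 14 to 22% below the true SD. If that were the only fault, the error would be 2Φ(−1.96 × 0.86) = 2Φ(−1.69) ≈ 9% to 2Φ(−1.96 × 0.78) = 2Φ(−1.53) ≈ 13%. The noise in the SE adds the rest.

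**6. Partial repairs, month indicators.** An n/(n−1) multiplier scales the SE by √(9/8) = 1.06. The shortfall calls for 1/0.86 = 1.16 to 1/0.78 = 1.28. With the multiplier alone the error is about 11 to 15%; with a t reference alone (7 or 8 df) it is about 7 to 12%. The two together, with 7 df, give 6.3 to 8.6%.

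**7. Linear time.** At flat incidence the error is 11.7 to 14.2%. With assumed peaks it is 5.3 to 13.8%. Across the wider settings it runs from 3.9% (sharply peaked season) to 18.2% (three steps). Under the assumed peaks the mean log RR with no effect is +0.04 to +0.12, a spurious RR of e^0.04 = 1.04 to e^0.12 = 1.13, because a straight line cannot follow the peak.

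**8. Coverage at RR 0.50, month indicators, uncorrected.** 86.7, 86.4 and 85.1% for the three size assumptions.

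**9. Corrected methods, month indicators.** Mancl-DeRouen variance with t(7) rejects about 3 to 5%, Kauermann-Carroll with t(7) about 5 to 8%, and a randomisation test over start months about 4 to 5%. Coverage at RR 0.50 is 96.8 to 97.0% for Mancl-DeRouen and 95.6 to 95.9% for the inverted randomisation test.

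**The case against.** The strongest reply is that Section X never says the variance is uncorrected or that a normal reference is used. That is right. A reader might infer that the plan prescribes a test with a 12 to 18% error rate; the documents support only an omission, and the figures apply if the omission is filled with the plain default.

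A reader might also infer that the error cannot be 5% under any reading. That is firm for month indicators only. Section X permits linear time, and some peaked seasons then give an error at or near nominal, even with few corrections. This is no reassurance, because the estimate is then biased.

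A third tempting inference is that the model itself is undetermined. Sections III and X both name a mixed model and Section X attaches the robust variance to it. Only the sample-size wording in Section IV differs, and it needs reconciling.

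Nor do the documents support blaming the Year 1 restriction alone. Section II plans "re-randomization of the shelters each season for timing of the intervention", so the same nine shelters would recur. Clustering two seasons by shelter gave 12.7 to 15.8%. Counting 18 shelter-season clusters gave 9.7 to 11.7%, which is better but still high.

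Two further points stand. The choice among corrected methods is partly preference, and no bias-corrected variance was tested for the mixed model itself. In an extreme case (RR 0.20, about 16 cases) the corrected CIs covered only 87 to 88% among the half of runs in which the RR could be estimated. At RR 0.50 with about 19 cases, the inverted randomisation CI covered 96.2%.

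**Conclusion.** The concern holds as an omission that decides whether the trial's only modelled result is valid. If the gap is filled with an uncorrected shelter-level robust variance and a normal reference, month indicators give a false-positive rate of roughly 12 to 18%. That is 12/5 = 2.4 to 18/5 = 3.6 times the nominal level, with CI coverage of about 85 to 87% at RR 0.50. Neither a t(7) reference alone nor an n/(n−1) multiplier alone restores 5% with month indicators. With linear time the error is about 4 to 18%, depending on season shape and steps, and a near-nominal figure under a seasonal peak comes with a biased estimate.

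All of these figures are approximate, since they rest on the assumed steps, periods, season shapes and shelter sizes. The excess appeared in every month-indicator setting tried. Nothing here shows that any reported result is wrong.

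**What to change.** In Section X, state:
1. month indicators for calendar time;
2. clustering of the robust variance by shelter;
3. one small-sample method that supplies both the p-value and the CI.

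Two methods would serve, and one must be named before its result is computed:
- A Poisson marginal model with log-capacity offset, a bias-corrected shelter-clustered variance and t on 7 df. Mancl-DeRouen is the conservative choice; Kauermann-Carroll loses less power but can run slightly above 5%.
- A randomisation test that re-assigns shelters to start months under the actual allocation scheme, with the CI by inversion and the RR point estimate from the fitted Poisson model.

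Reconcile the estimating-equation wording in Section IV with Sections III and X. Label the change as a dated correction made after the primary data window closed, and report the mixed-model result that Section X now specifies alongside it.

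This takes an amendment and code, and no new data. The price is wider intervals and lower power. For RR 0.50, one season and 200 per shelter, power is about 71 to 73% uncorrected (inflated by its own error rate). Corrected, it is 52 to 55% for the randomisation test, about 52% for Kauermann-Carroll and 37 to 42% for Mancl-DeRouen. With 114.7 per shelter the uncorrected, randomisation and Mancl-DeRouen figures are 55, 34 and 24%. CIs remain approximate at very low case counts, and the report should say so.
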